#### 2. STUDY DESIGN

#### 2.1 INCLUSION AND EXCLUSION CRITERIA

#### Inclusion criteria:

- Patients' data entries from ISAR who are from countries that have at least two biologics available (defined as the presence of a license for the treatment of severe asthma),
- Patients, 18 years of age or older, with a diagnosis of severe asthma which requires treatment with guideline-suggested medications with 2018 GINA:

Study Protocol: [OPCG-2005] Biologic Usage Patterns, Clinical Outcomes and Healthcare Resource Utilization (CLEAR)

- Treatment Step 4 and being uncontrolled OR
- Treatment Step 5.
- Registry data for a minimum of one year prior to index date (defined as the date of biologic initiation for biologic patients and date of ISAR enrolment for non-biologic patients) and 24 weeks after therapy or enrolment,
- Data received by ISAR before July 2021

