#### Did not initiate:

- Not eligible: Did not meet the criteria for eligibility of biologic therapy and did not initiate any therapy
- Eligible: Eligible for biologic therapy but did not initiate any biologic therapy
- A "frequent-eligibility" criterion of each biologic class will be used to assess eligibility. This
  criterion will be constructed using the results from the ISAR biologic availability survey and
  will be subject to confirmation from the ISAR scientific steering committee (see Table 1 for
  possible criteria per biologic class)

[figure not shown]

Table 1: Frequent-Eligibility Criteria per Biologic Class. Patients who did not initiate biologic therapy and are eligible will meet any of the three criteria for any of the three biologic groups.

	Anti-lgE	Anti-IL5/5R	Anti-IL4/13
Background therapy	Met via ISAR inclusion criteria		
Positive Allergen test	Yes, AND	N/A	N/A
IgE levels	≥ 30 IU/mL, AND	N/A	N/A
BEC	N/A	≥ 150 cells/µL with long- term OCS, OR ≥ 300 cells/µL without long-term OCS, AND	≥150 cells/µL with long-term OCS, OR ≥300 cells/µL without long-term OCS, OR
FeNO	N/A	N/A	≥25 ppb, AND
Exacerbation OR Iong-term OCS	Pre-therapy exacerbation (≥2) OR On long-term OCS	Pre-therapy exacerbation (≥2) OR On long-term OCS	Pre-therapy exacerbation (≥2) OR On long-term OCS

The ISAR enrolment date will mark the start of the outcome period for those who did not initiate biologics while for those who did the index date will be signified by the First Biologic Therapy Start Date. A minimum of 16-weeks of follow-up time post biologic initiation (outcome period) will be applied in alignment with the ERS recommendation for time of biologic response assessment [8]. This is also congruent with the methodology used in the ISAR research project 'Defining and Characterizing Responders to Biologic TrEAtment in Severe AsthMa Patients (BEAM).' To assess the impact of this design, the study will evaluate and report the number of patients that had three types of follow-up data: 1.) <24 weeks, 2.) > 24 weeks to 1-year 3.) >1-year.

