#### 3.2 STUDY OUTCOMES

The following outcomes measures are measured after index date (follow-up visits).

Table 3 Clinical outcomes of interest for objective 2 of the study

Variable Name	Туре	Description
Number of annualized asthma exacerbations 	Count	Annualized number of exacerbations requiring rescue steroids after index date
Asthma control in the past 4 weeks	Categorical	Categorized as controlled, partly controlled, or uncontrolled according to the GINA Asthma Control Criteria/Asthma Control Questionnaire (ACQ-6)/Asthma Control Test (ACT)
Total dose of oral corticosteroids 	Continuous	Label Dose X Frequency X Duration of Use for maintenance OCS between the index date and date of data extraction
Number of hospital admissions	Count	Annualized number of hospital admissions after index date
Number of emergency room visits	Count	Annualized number of emergency room visits after index date

<sup>3 Total number of exacerbations will be calculated between index date and current visit date

<sup>4 If use of SCS started after the index date, total dose will be calculated between start- and end date of use

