**Primary outcome: Exacerbation** 

An asthma exacerbation will be defined as the occurrence of the following events (ERS/ATS task

force definition):

asthma-related hospital attendance/admission primary care consultation; AND/OR

asthma-related A&E attendance; AND/OR

an acute oral corticosteroid course of 3 days or more

separate recordings of exacerbations within a 14 day period will be treated as the

same exacerbation.

A time-to-event analysis will be performed to analyse the association between utilization pattern and time to first exacerbation with right censoring at the time of death, switching, stopping or loss to follow-up. Kaplan-Meier curves will be used to describe event-free survival over time and comparisons. Conditional Cox regression will be performed with time to the first exacerbation as the outcome variable (y) to estimate Hazard Ratios (HR) with 95% confidence intervals (CI) of the main effect. The proportional hazard assumption will be evaluated visually by means of a log-log

plot of survival.

As the dispersion of the exacerbation data is expected to be high and as this outcome is conditional on the duration of follow-up, we may apply a negative binomial regression (NBR) to estimate the reduced rate of exacerbation (y=annual rate of exacerbation). We switch to a count model to take advantage of all exacerbations at follow up. Group comparisons (e.g. gender, BMI, number of biologics available etc.) will be made if interaction between a group and biologic use pattern is found. We will also run a NBR using the total post-therapy/post-ISAR enrolment

exacerbations.

Secondary outcome: Asthma control

By applying a multinomial regression model (ordered), we will assess the probability or odds of the combined categories partially or controlled versus uncontrolled asthma for those that continue

compared to those that do not initiate or switch or stop.

Secondary outcome: long term oral corticosteroid (OCS) dose

20

Study Protocol: [OPCG-2005] Biologic Usage Patterns, Clinical Outcomes and Healthcare Resource Utilization (CLEAR)

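### Non-initiators are defined by never starting a biologic but followed from enrolment, so patients whose worsening leads to a biologic drop out of the comparator with their untreated exacerbations

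*Protocol*

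**What the plan says.** - **Groups (Protocol 2.2, Did not initiate).** There are two non-initiator groups, eligible and not eligible. The first reads "Eligible: Eligible for biologic therapy but did not initiate any biologic therapy". Neither definition says over what period non-initiation is judged.
- **Time zero (2.1).** The index date is "defined as the date of biologic initiation for biologic patients and date of ISAR enrolment for non-biologic patients". Section 2.2 repeats this for the comparator: "The ISAR enrolment date will mark the start of the outcome period for those who did not initiate biologics".
- **Minimum follow-up (2.1).** Registry data are required for one year before index "and 24 weeks after therapy or enrolment".
- **Outcome window (3.2, footnote 3 to Table 3).** "Total number of exacerbations will be calculated between index date and current visit date".
- **Eligibility (2.2, Table 1).** Every biologic class requires "Pre-therapy exacerbation (≥2) OR On long-term OCS". The table is presented as possible criteria, subject to steering committee confirmation.
- **Comparison (4.2, Group comparisons).** Initiators against non-initiators is the first set of results for the primary and secondary outcomes.
- **Censoring (4.2, Primary outcome).** Time to first exacerbation is analysed "with right censoring at the time of death, switching, stopping or loss to follow-up". Starting a first biologic is not listed.
- **Adjustment (4.2).** Propensity-score matching on baseline characteristics, with residual imbalance entered in the model.

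**The concern.** The index date cannot be set until the group is known, and the group depends on whether a biologic is ever started. For a patient enrolled untreated, that is settled only after enrolment.

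Take a patient who enrols untreated, exacerbates repeatedly for 18 months and then starts a biologic. Under 2.1 the index date is the biologic start. The 18 untreated months and their exacerbations precede index and never count as non-initiator outcome. A patient who enrols on the same day and stays well remains in the comparator with all follow-up counted. If worsening makes a start more likely, the comparator is enriched for patients who did well.

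The comparison affected is the first one the protocol reports. The same mechanism applies to the not-eligible group, whose members can become eligible by exacerbating. The protocol sees a related problem in 2.2, where stoppers may be on the way to switching, and plans a safeguard for it. It has none for non-initiators on the way to initiating.

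**Working it through.** **No figure to reproduce.** The protocol gives no untreated exacerbation rate, no number of patients starting after enrolment and no probability that an exacerbation leads to a start. All inputs below are assumptions.

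**Model.** Exacerbations follow a Poisson process from enrolment with patient rate r. After each one a biologic is started with probability q. A patient followed for time T remains a never-initiator with probability exp(−q·r·T).

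**Case 1: all patients share one rate.** Among never-initiators the exacerbations are a thinned process with rate (1−q)·r, so

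observed / true = 1 − q = 0.95, 0.90, 0.80 for q = 0.05, 0.10, 0.20.

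**Case 2: rates differ between patients.** Section 4.2 expects high dispersion, so this case is relevant. Let r be gamma with mean m and shape k. For fixed T,

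observed / true = (1−q) / (1 + q·m·T/k).

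With m = 1 per year, frailty variance 0.8 (k = 1.25) and T = 1 year:
- q = 0.05: 0.95 / 1.04 = 0.91
- q = 0.10: 0.90 / 1.08 = 0.83
- q = 0.20: 0.80 / 1.16 = 0.69

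Simulation with 200,000 patients per scenario gives the same values.

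**Case 3: variable follow-up.** Let T be uniform from 24 weeks to 5 years. Dividing total events by total person-time among never-initiators gives

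observed / true = (1−q) · ∫T(1+qmT/k)^−(k+1) dT / ∫T(1+qmT/k)^−k dT.

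| Scenario | q = 0.05 | q = 0.10 | q = 0.20 |
|---|---|---|---|
| One common rate | 0.95 | 0.90 | 0.80 |
| Mean 1 per year, shape 2 | 0.88 | 0.78 | 0.61 |
| Mean 2 per year, shape 1 | 0.72 | 0.56 | 0.38 |

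The 0.38 needs about half of the untreated enrolees (49%) to start a biologic during follow-up.

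**Time to first exacerbation.** With m = 1, k = 1.25, T = 1 year and q = 0.20:
- all untreated patients: 1 − (1 + 1/1.25)^−1.25 = 52% have an exacerbation
- never-initiators: 1 − [(1 + 1/1.25) / (1 + 0.2/1.25)]^−1.25 = 42%

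**Negative control.** With a background start hazard of 0.2 per year unrelated to exacerbations and q = 0, the ratio is 1.00. Only outcome-driven starts after enrolment bias the rate.

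**Effect of the repair.** Keep all untreated patients and censor at first biologic start. With a common rate the ratio is 1.00. With m = 1, k = 1.25 and T = 1 year it is 0.98, 0.96 and 0.93 for q = 0.05, 0.10 and 0.20, against 0.91, 0.83 and 0.69 without the repair. The rest is informative censoring.

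**The other reading.** Suppose non-initiation means status at enrolment. Later starters then stay in the comparator, and because 4.2 does not censor at first biologic start, treated time counts as untreated. That also conflicts with 2.1, since these patients have a biologic start date that should be their index.

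**The case against.** Several points on the other side are fair.

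- **The definition carries no time window, so reading it over the whole record is inference.** This stands. A reader might take the missing censoring event as proof of that reading. It is not: it fits equally well with classification at enrolment or with a loosely written list. The stronger support is the group-dependent index date. Some design figures are not shown and might bear on this.
- **Table 1 is not a new gateway for eligible non-initiators.** This stands. A reader might infer that a further exacerbation opens access for them, but they already meet the criterion. That route fits the not-eligible group. Table 1 is also a provisional study definition, not a description of prescribing in the 22 listed countries, and the protocol itself names availability and access as main confounders. How closely starts follow exacerbations is unknown.
- **Only starts after enrolment matter.** This stands. The registry holds retrospective data, so some initiators may have started before enrolment.
- **The net direction is not fixed.** A reader might infer that the result will certainly lean toward no benefit or harm. The documents do not show this: the downward bias in the comparator is conditional, and the six months of use required of continuers also selects on later events, in the other arm.
- **Matching may help.** It can reduce the part due to stable differences between patients if baseline variables capture them. It cannot remove the 1 − q component, which arises after index.
- **Censoring detail belongs in the SAP.** The SAP is not at hand and may refine it. Group definitions and index dates, however, are fixed in this protocol.

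**Conclusion.** The concern holds in conditional form. As written, 2.1 and 2.2 make membership of both non-initiator groups depend on events after their index date, in the period over which their exacerbations are counted, and nothing in 4.2 corrects for it. To the extent that starts after enrolment follow worsening, the untreated rate is too low and the initiator versus non-initiator comparison is biased against the biologic by this mechanism. Starts before enrolment, or unrelated to outcome, do not bias the rate. Reading the definition as status at enrolment exchanges this fault for treated time counted as untreated, and calls for the same change.

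The size is unknown. The scenarios in the table run from 0.95 to 0.38 of the true rate and are illustrative only. A reader might take the lowest value as an estimate; nothing in the protocol supports that, since it rests on a high mean rate, strong heterogeneity, follow-up to five years and about half of untreated enrolees starting a biologic.

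**What to change.** For the initiator versus non-initiator outcome comparison, amend 2.2 and 4.2 as follows.

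1. Define non-initiator status and eligibility at enrolment, from information available then.
2. Let every biologic-naive patient contribute untreated time from enrolment to first biologic start, and enter the initiator group from that date. The minimum follow-up should not require that this time stay untreated, which would bring the selection back.
3. Add first biologic initiation to the censoring events for the untreated state.
4. Use patient-clustered standard errors, and inverse-probability-of-censoring weights or a sensitivity analysis, because simple censoring leaves some bias under heterogeneity.
5. Keep the five never/ever groups for the descriptive objective 1.
6. Report how many patients start after enrolment, so that the size of the problem can be seen.

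**Cost.** Biologic start dates are already used to set the index date, so no new data collection is apparent. The work is protocol wording and extra programming, including adapting the matching and the conditional Cox model for this one comparison. Some patients count in both states, and residual informative censoring remains if the weights miss drivers of initiation.

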First the demographic and clinical characteristics as mentioned in section 3.1 will be described in detail per group. This will include describing proportions on patients from each group based on their biomarkers, long term OCS (LTOCS) use, baseline demographics such as those outlined in Section 3.1. Next, the significant difference in level of T2 phenotypes and demographic or clinical characteristics (section 3.1) across the five groups will be compared and tested for statistical significance via Chi-square tests for comparison of counts data, and t-test or one-way analysis of variance (ANOVA) for continuous variables. Where appropriate, McNemar tests, paired t-tests will be considered. Statistical significance will be defined as p <0.05. Stata version 14.2 (College Station, TX, USA) will be used to conduct all statistical analyses and data manipulations.

Additionally, comparisons will be made as follows:

Study Protocol: [OPCG-2005] Biologic Usage Patterns, Clinical Outcomes and Healthcare Resource Utilization (CLEAR)

- 1. Switch vs. continue
- 2. Stop vs. continue
- 3. Patient received biologics vs. eligible but did not receive biologics
- 4. Biologic eligible (biologic users+ non-users but who qualify) vs. not eligible.

#### 4.2 OBJECTIVE 2

As there are various factors underpinning the probability of not receiving, receiving, continuing, switching, or stopping a biologic, comparing the clinical outcomes set forth in section 3.2 will need careful consideration. One of the main confounders to consider is the availability and/or accessibility of multiple biologics in a country. Therefore, all countries included in the analysis of assessing the clinical outcomes across biological utilization groups will have at least 2 biologics available in the market (availability defined as licensed in the country) at the time of the patient's enrolment into ISAR (index date). There will be a cut-off date of 01 Jan 2014 for assessment of clinical outcomes to ensure the availability of drugs in the market.

Furthermore, according to the results of objective 1 (pre-therapy or baseline characteristics), before assessing for differences in the clinical outcomes across groups, baseline imbalance will be examined across groups and matched accordingly. Prior to this step, the clinical outcomes of each group will be described.

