Steroid-sparing agent (specific drug can be found in current medication)
Enter into clinical trial
Other (please specify)

\*CAP immunoCAP test, CT computed tomography, DEXA dual energy X-ray absorptiometry, ELISA enzyme-linked immunosorbent assay, FeNO fractional exhaled nitric oxide,  $FEV_1$  forced expiratory volume in 1 second, FVC forced vital capacity, GINA Global Initiative for Asthma, ICS inhaled corticosteroids, IgE immunoglobulin E, IL-5 interleukin-5, ISAR International Severe Asthma Registry, LABA long-acting  $\beta_2$ -agonist, LAMA long-acting muscarinic antagonist, LTRA leukotriene receptor antagonist, PC20 provocative concentration of methacholine/histamine needed to produce a 20% decrease in  $FEV_1$ , PEF peak expiratory flow, RAST radioallergosorbent test, SPT skin prick test.

Asthma Control Questionnaire or the Asthma Control Test are optional extras for this category (depending on registry preference).

Other new biologics will be added once approved and in use.

Poor adherence to treatment can be indicated by selecting either (a) or (b):

[figure not shown]
- (a) Clinical impression: opinion of a medical personnel
  - E.g. i) Impression of 'non-persistence': patient stops taking medication.
  - ii) Impression of 'non-conformation': patient does not take medication as prescribed.
- (b) Prescription records: evidenced by medical records detailing prescriptions being issued and inadequately filled.
  - E.g. Medication possession ratio (MPR) = (Sum of days' supply for all fills/Number of days) x 100% <80% threshold.

Calls for a trained clinician's perception or opinion on any other external factors (if any) potentially contributing to the severe asthma symptoms.

E.g. Weather (cold air), air pollution, physical activity (exercise-induced asthma symptoms), occupational triggers (workplace irritants, gases, chemical fumes, dust), strong smells (perfumes), prior respiratory infections.

Aims to record the asthma action plan for a patient to review efficacy over time.

- E.g. i) Entry into clinical trial: If patient can benefit from a clinical trial drug.
- ii) Discharge to local asthma service: If patient has shown alleviated asthma symptoms.
  - iii) Optimisation of current asthma therapy: If patient's current asthma therapy is titrated for better asthma management.
- iv) Bronchial thermoplasty: If patient is eligible to have a surgery to manage their asthma.

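### Table 1 counts a non-initiator as eligible through any of three biologic classes without asking whether that class was licensed in the patient's country at index, so objective 1 may mix lack of access with non-use

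*Protocol*

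**What the plan says.** Section 2.2 defines the group only by criteria met and treatment not started: "Eligible: Eligible for biologic therapy but did not initiate any biologic therapy". Table 1 gives one set of criteria for each of three classes (anti-IgE, anti-IL5/5R, anti-IL4/13), and its caption states "Patients who did not initiate biologic therapy and are eligible will meet any of the three criteria for any of the three biologic groups". The criteria are provisional. Section 2.2 says that the "criterion will be constructed using the results from the ISAR biologic availability survey and" are subject to steering committee confirmation.

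Licensing enters only at country level. Section 2.1 admits patients from "countries that have at least two biologics available (defined as the presence of a license for the treatment of severe asthma"), with no date attached. Section 4.2 repeats the condition for the outcome analysis, where countries "will have at least 2 biologics available in the market (availability defined as licensed in the country) at the time of the patient's enrolment", and adds a cut-off of 01 Jan 2014. The same section names availability of multiple biologics as a main confounder.

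The label is used directly in two of the additional comparisons in Section 4.1: comparison 3, "Patient received biologics vs. eligible but did not receive biologics", and comparison 4, which sets all eligible patients (users plus qualifying non-users) against those not eligible.

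**The concern.** Both filters count biologics, whereas Table 1 works by class. Two licensed biologics can leave a third class unlicensed. They can also belong to a single class: Table S1 lists three named products under the one anti-IL-5/5R field. A patient may then satisfy the criteria of a class that had no licensed product in that country and satisfy no other class.

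The two arms of comparison 3 are not treated alike in this respect. Initiators are taken to be eligible because they started a biologic (note to Figure 2, Section 1.2), so each had a product within reach. Non-initiators are eligible by profile alone. If some of them had no licensed product in a class they qualify for, the comparison partly contrasts access with no access instead of use with non-use. Section 1 says the study is looking for patients who are eligible and yet do not benefit from targeted therapy, so the reader needs to know which kind of patient the group contains. Objective 1 also describes biomarkers by group, and the affected patients would have particular biomarker profiles.

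**Working it through.** The protocol gives no figure for this point, so there is none to reproduce. The check is a logical count of Table 1 profiles.

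**Inputs (Table 1).** Allergen test positive or not (2); IgE at least 30 IU/mL or not (2); BEC below 150, 150–299, or at least 300 cells/µL (3); FeNO at least 25 ppb or not (2); at least two exacerbations or not (2); long-term OCS or not (2). Profiles: 2 × 2 × 3 × 2 × 2 × 2 = 96.

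**Reading of the table.** All conditions within a class column must hold, and meeting one column is enough. The anti-IL4/13 column is read as (BEC or FeNO) and (exacerbations or OCS).

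**Count of eligible profiles.**
- Every column needs exacerbations or OCS: 3 of the 4 combinations. With three BEC levels this gives 3 × 3 = 9 combinations.
- BEC criterion met: with OCS, 2 BEC levels × 2 exacerbation states = 4; without OCS but with exacerbations, 1 level. Total 5 met, 4 not met.
- The anti-IgE biomarker pair (positive test and IgE) is met in 1 of 4 combinations and not met in 3.
- Profiles with exacerbations or OCS: 9 × 2 × 4 = 72. Of these, the ones meeting no column have BEC not met (4), FeNO low (1) and anti-IgE not met (3): 4 × 1 × 3 = 12.
- Eligible: 72 − 12 = 60.

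**Profiles with a single route to eligibility.**
- Only anti-IL4/13: BEC not met, FeNO high, anti-IgE not met: 4 × 1 × 3 = 12.
- Only anti-IgE: BEC not met, FeNO low, anti-IgE met: 4 × 1 × 1 = 4.
- Only anti-IL5/5R: 0, because the BEC limits are the same in both columns and any profile meeting anti-IL5/5R also meets anti-IL4/13.

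**Eligible profiles with no licensed qualifying class.**

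| Classes licensed in the country | Affected, of 60 |
|---|---|
| All three | 0 |
| Anti-IgE and anti-IL4/13 | 0 |
| Anti-IL5/5R and anti-IL4/13 | 4 |
| Anti-IgE and anti-IL5/5R | 12 |
| Anti-IL5/5R only (both biologics in one class) | 20 |

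The last row is the BEC-not-met profiles that qualify through FeNO or anti-IgE: 4 × (4 + 1) = 20.

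The two-biologics filter permits every row of this table, so it does not close the gap. The profiles are not weighted by how common they are, so 12 of 60 must not be read as 20% of patients.

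**The case against.** The strongest reply is that frequent eligibility is meant as a uniform clinical and biomarker standard. Table 1 has no access item, and Section 1 mentions accessibility and eligibility as separate hurdles. On that reading, a patient who meets the criteria but lacks access belongs in the group. This is a fair reading and it stands in part: it is a reason not to remove these patients from the group or create a sixth one. It does not remove the ambiguity, because the protocol never states that meaning, draws its criteria from an availability survey, and itself calls availability a main confounder.

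Four stronger readings are tempting, and the protocol does not support them:
- A reader might infer that patients who could not be prescribed any biologic are counted as eligible. Countries with fewer than two licensed biologics are excluded, so the most that can be said is that no class whose criteria the patient meets was licensed.
- A reader might infer that the protocol shows a class was missing for included patients. Table S1 lacks an anti-IL4/13 field, and its footnote says "Other new biologics will be added once approved and in use", but both concern registry data fields, not national licences.
- A reader might infer a fixed shift toward high FeNO with low eosinophils. That holds only where anti-IL4/13 is the missing class. Where anti-IgE is missing, the affected profiles are allergic with low FeNO.
- A reader might infer that the main outcome results are biased. The group comparisons in Section 4.2 pool all non-initiators against initiators, then compare those who stopped or switched with those who continued. Neither contrast uses the label.

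**Conclusion.** The concern holds in a limited form. The eligibility rule is not tied to a licence for the qualifying class, and filters that count biologics cannot guarantee one. Comparison 3 is the most exposed, and as an objective 1 comparison it has no licensing filter dated to index. Comparison 4 is less exposed, since its eligible arm also contains all biologic users and Section 2.4 says most study patients initiated and continued.

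Between 0 and 12 of 60 eligible profiles are affected when two or three classes are licensed, and 20 of 60 if both licensed biologics are anti-IL5/5R. This rests on the column-by-column reading of Table 1. The protocol gives no licence data by class and country and no distribution of profiles, so neither the number of patients nor a percentage overstatement of the untreated group can be stated. This is a cheap improvement to the plan, not a flaw that invalidates the study.

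**What to change.** Keep the five groups and Table 1. Add a flag for each eligible non-initiator: was at least one class whose criteria the patient meets licensed for severe asthma in the patient's country on the index date (ISAR enrolment for these patients)? Report the two subsets separately in the objective 1 tables, and repeat comparisons 3 and 4 with the eligible non-initiators restricted to those with a licensed qualifying class. State in Section 2.2 that eligibility means meeting the Table 1 criteria irrespective of licensing, if that is the intent.

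The Section 4.2 filter already needs to know which biologics were licensed in each country at enrolment, so the flag requires only that these be sorted by class. Table 1 still awaits steering committee confirmation, so the change can be made at that step. The cost is a smaller eligible, non-initiated group in the restricted analysis and a little more analysis work. A licence does not prove access, so the flag narrows the ambiguity without removing it.

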#### 2.3 DATA SOURCE

The ISAR registry is a multi-country, multi-center, observational epidemiologic data repository with retrospective and prospective data of patients treated with 2018 Global Initiative for Asthma (GINA) Step 5 or uncontrolled on GINA Step 4 treatment regimens. ISAR holds standardized, patient-level, fully anonymized data for ~9,654² (as of November 2020) patients with severe asthma from 19 national registries (Argentina, Australia, Bulgaria, Canada, Colombia, Denmark, Greece, India, Ireland, Italy, Japan, Kuwait, Mexico, Saudi Arabia, South Korea, Spain, Taiwan, UAE, UK and United States). The data is collected specifically for severe asthma research. All data contributors enter data via electronic Case Report Forms (eCRF) on a web-based platform customized for real-life data collection or within specialized electronic medical records. The reason for either stopping or switching the first biologic is also collected, when applicable [4]. Patient recruitment started in December 2015 Ethical governance for ISAR is provided by The Anonymous Data Ethics Protocols and Transparency (ADEPT) committee, an independent body of experts and regulators commissioned by the Respiratory Effectiveness Group (REG). The registry's scientific merit is ensured by the ISAR steering committee (ISC) that is made up of 48 severe asthma specialist or database experts from 25 countries (http://isaregistries.org/)

<sup>2 This does not include the 671 patients from the Australian Severe Asthma Network that was received on the 1st of Dec. as it is undergoing data quality assessments at the moment.

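### Initiators' outcome time may begin before ISAR enrolment, so part of it depends on surviving and probably still having severe asthma at enrolment, and stoppers who did well are probably under-represented

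*Protocol*

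**What the plan says.** Time zero differs by group. Section 2.2 follows non-initiators from the day they enter ISAR. Its rule for initiators is different: "for those who did the index date will be signified by the First Biologic Therapy Start Date". The inclusion criteria in section 2.1 and the opening of section 3 use the same two definitions. Section 4.2, in its rule on countries with at least two biologics, instead labels ISAR enrolment as the index date.

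Section 2.3 describes the registry as holding "retrospective and prospective data of patients treated with 2018 Global Initiative for Asthma (GINA) Step 5 or uncontrolled on GINA Step 4", and adds: "Patient recruitment started in December 2015". Section 4.2 states: "There will be a cut-off date of 01 Jan 2014 for assessment of clinical outcomes". Section 2.1 limits the data to those that reached ISAR before July 2021.

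The time-to-event paragraph in section 4.2 censors on the right at death, loss to follow-up, stopping or switching. It mentions no entry time later than the index date. Stoppers are defined in section 2.2 without any condition that the stop follows enrolment. The footnotes to Table S1 record a route out of specialist care for patients who do well: "Discharge to local asthma service: If patient has shown alleviated asthma symptoms".

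**The concern.** A patient who starts a biologic before enrolment is in the data only if alive at enrolment and, as the registry population is described, probably only if still at Step 5 or uncontrolled at Step 4. The plan nevertheless counts the interval as follow-up. That is left truncation, and it may be related to the outcome.

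Two comparisons are exposed. Non-initiators have no interval between index and enrolment, so initiators carry conditional time that their comparators lack. Within initiators, continuers are on a biologic and will generally still qualify, whereas a stopper who became controlled at Step 4 or below before enrolment would not. A stopper who stayed severe would. Propensity matching does not address this, because it uses values at or before the index date and the selection happens afterwards.

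**Working it through.** **Figures in the plan.** The protocol gives no event rate, effect size or power statement, so there is no design figure to reproduce. Section 1 cites an earlier ISAR study in which 2791 patients continued, 356 stopped and 384 switched. These sum to 3531 and give 79.0%, 10.1% and 10.9%, matching the stated 79, 10 and 11%. Stoppers are thus a small group in which selective loss would matter.

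**Does the look-back prevent the problem?** Section 2.1 requires: "Registry data for a minimum of one year prior to index date (defined as the date of biologic initiation for biologic patients", with enrolment as the index for everyone else. For non-initiators the required year ends at enrolment, so it can be met only with retrospective data. Initiators fall under the same wording, so it does not force their enrolment to precede biologic start.

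**Calendar check.** From 01 Jan 2014 to 1 December 2015 is 699 days; to 31 December 2015, 729 days. Dividing by 30.4375 gives 23.0 to 24.0 months. From 01 Jan 2014 to 1 July 2021 is 2738 days, and 699/2738 = 25.5%, 729/2738 = 26.6%. About a quarter of the calendar span open to outcomes therefore lies before anyone could have been recruited. Later biologic starts can also precede a patient's own enrolment.

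**Which analyses are exposed (section 4.2).**
- Cox model: follow-up is censored at stopping, so events after a stop do not enter. Pre-enrolment time for initiators still does.
- Negative binomial models: these are meant to use all exacerbations in follow-up, including a total after therapy start, so both pre-enrolment and post-stop time count.
- Asthma control is assessed after the index date. Resource use is analysed like exacerbations, so its count analyses share the exposure.

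**Illustration of size; every input is assumed.** Let *w* be the share of stoppers who do well, *e* the share who stop before enrolment, *m* the share of well-doing pre-enrolment stoppers who never enrol, and *rl* = 0.5 and *rh* = 2.0 the yearly exacerbation rates of those doing well and badly. Continuers are taken to have the stoppers' true rate and no selection.

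True rate = *w*·*rl* + (1 − *w*)·*rh*

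Observed rate = [*w*(1 − *em*)·*rl* + (1 − *w*)·*rh*] / [*w*(1 − *em*) + 1 − *w*]

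| *w* | *e* | *m* | True | Observed | Apparent rate ratio |
|---|---|---|---|---|---|
| 0.2 | 0.25 | 0.25 | 1.70 | 1.715 | 1.01 |
| 0.2 | 0.5 | 1.0 | 1.70 | 1.833 | 1.08 |
| 0.4 | 0.25 | 0.5 | 1.40 | 1.447 | 1.03 |
| 0.4 | 0.5 | 1.0 | 1.40 | 1.625 | 1.16 |

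For the last row, *w*(1 − *em*) = 0.4 × 0.5 = 0.2, so the observed rate is (0.2 × 0.5 + 0.6 × 2.0)/0.8 = 1.625, and 1.625/1.40 = 1.16. With *e* = 0, meaning no stops before enrolment, the ratio is 1.00.

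**The case against.** The case against is substantial in several respects.

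- *The 2014 date.* A reader might infer that biologic starts are accepted from 01 Jan 2014, giving 23 months of pre-recruitment index dates. The text sets a cut-off for outcome assessment, not a window for index dates. What stands is narrower: outcome time before recruitment is admissible.
- *The index label in 4.2.* If enrolment really were the index for the outcome analysis, the pre-enrolment interval would disappear. But sections 2.1, 2.2 and 3 all say biologic start for initiators. The conflict is itself something to resolve.
- *The entry condition.* No section says that severity is judged on the enrolment date, and ISAR is built from national registries whose own follow-up is not described. Conditioning on severity is therefore probable rather than stated.
- *Stoppers who did well.* A reader might infer that they are missing altogether. They are not: anyone enrolled before stopping remains, and Step 5 patients qualify whatever their control. Section 1 gives lack of efficacy and adverse events as the most common reasons for stopping or switching, so stoppers who did well may be few.
- *Direction.* A reader might infer a definite bias toward harm from stopping. Deaths between start and enrolment are also unseen and could act the other way, and the Cox model drops post-stop events.
- *The analysis plan.* Entry-time handling can be left to an analysis plan that is not shown, and the design figure is also not shown. However, this protocol itself fixes the time origins and the outcome window, and does so inconsistently.

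**Conclusion.** The point holds as a design weakness of unknown size. As written, initiators' outcome time can include an interval in which they had to survive, and probably had to remain severe, in order to be observed. Non-initiators have no such interval, and stoppers who did well before enrolment are probably under-represented.

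Bias toward harm from stopping is likely but not established. The share of initiators who started before enrolment is not given, so the range of 1.01 to 1.16 shows only what the assumed inputs produce. A reader might also compute that a loss of 10 to 30% of stoppers per year over two years removes 19 to 51% of them (1 − 0.9² and 1 − 0.7²). The documents support neither the yearly loss nor the two-year gap, and a share removed is not a bias in an estimate.

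**What to change.** 1. State one index definition and reconcile section 4.2 with sections 2.1, 2.2 and 3.
2. In section 4.2, let initiators' at-risk time and events begin at the later of first biologic start and ISAR enrolment: delayed entry in the Cox model and the same exposure start in the count models. Use earlier exacerbations as history. Define the first exacerbation as the first after entry, so that an earlier event does not remove the patient.
3. Prespecify a sensitivity analysis limited to initiators whose first biologic start is on or after enrolment. It is needed because delayed entry removes the conditional time but cannot recover stoppers who never enrolled.
4. Report, by stop, switch and continue, how many initiators started before enrolment and the distribution of the gap. This will show whether the issue is trivial or material.

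The cost is protocol wording and an entry date in the model set-up; the plan already relies on both dates. The price is fewer person-years and events. In particular, initiators who stopped or switched before enrolment would contribute no time to a Cox model that censors at stopping or switching. The loss in the restricted set cannot be estimated from the protocol, which is why it is proposed as a sensitivity analysis and not as the only main set.
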